Covariates: Age, BMI, Diabetes, Duration of symptoms, Steroid use
Adverse events: Air leak, bleeding requiring transfusion, need for additional chest tube, and need for secondary operation/intervention, mortality

B. Description of Population to be Enrolled:

Adults ≥ 18 admitted with pleural effusion diagnosed by chest x-ray or computed tomography, that undergo thoracentesis or chest tube drainage by any service.

If the patient has a pleural fluid PH < 7.3 , the patient will be screened for potential study enrollment. If the patient does not have any exclusion criteria (listed below) the patient will be followed for study enrollment. If there is a persistent effusion 24 hours after chest tube insertion, diagnosed by morning chest X ray, and no exclusion criteria identified, the patient may then undergo CT scan to characterize the effusion. If CT scan is done and confirms a loculated fluid collection or if an additional CXR is grossly abnormal, despite chest tube drainage, these patients will then be approached for consent and randomized to either bedside fibrinolytic therapy through their chest tube versus operative VATS decortication. The patients that undergo VATS decortication, will subsequently be transferred to the surgery service for the remainder of their hospital stay.

Exclusion:

- Intrathoracic malignancy
- Any existing malignancy causing malignant effusion
- Prehospital pulmonary symptoms over 14 days prior to admission
- Prior instrumentation of the chest during same admission
- Malignant cells from initial pleural fluid sample
- End stage liver disease (Child's B or greater)
- Coagulopathy
- Unable to tolerate surgical procedure
- Frank purulent drainage (needs OR regardless)
- Recent surgery of abdomen or thorax precluding the use of tPA
- Pre-existing and permanent neurologic impairment

C. Study Design and Research Methods

This study is a proposed pragmatic prospective randomized open label clinical trial to treat patients with complicated parapneumonic effusion. Complicated parapneumonic effusion is defined as fluid collection in the pleural space with a fluid pH < 7.3 .

Standard of Care Procedure prior to study eligibility:

Patients with parapneumonic effusions identified on chest x-ray or CT will be admitted to the medicine service and started on the appropriate therapy. The medicine/pulmonary service will then perform a thoracentesis or place a chest tube in patients that there is a concern for an infectious process. Pleural fluid sampling will undergo pH testing, and those patients with a low pleural pH (pH <7.3) will continue to be observed over the next 24 hours. Those patients who have persistent fluid collections >24 hours from chest tube placement identified by a morning chest X ray, will undergo a CT scan of the chest to further characterize the pleural space. These eligible patients will be approached by a study team member for study consent to enroll and randomized into a treatment group (Fibrinolytic therapy vs. early VATS Decortication).

[figure not shown]
Study Procedures:

Eligible patients will be screened for study participation and after consenting will be randomized to early surgical decortication via VATs versus fibrinolytic therapy (FT) based off of the current MIST II protocol, currently utilized at Denver Health. Should the patient be randomized into the FT group, initiation of fibrinolytic therapy will start within 24 hours of CT scan. Conversely, if the patient is randomized into the surgery group, VATS decortication will occur as soon as the operating room is available. The fibrinolytic therapy will be delivered by a member of the treatment team per current standard of care for 3 days. Removal of chest tubes is dependent on the mutual agreement of both the surgical and pulmonary attending involved with the patients care. Per standard clinical care, labs will be collected daily (determined by the medical team, but usually include complete blood count and basic metabolic panel). In addition to the standard of care labs, pleural fluid will be collected for study purposes and extra blood samples will be collected for thrombelastography (TEG) analysis. TEG assesses changes in clot strength in both plasma and pleural samples by measuring proteins related to coagulation with proteomic analysis. Thrombo Therapeutics, Inc. is not involved in this study. tPA-challenged TEG assay is used for research purposes only. The data from this test is not accessible for the clinical care providers and does not affect the patient care. We are using this assay to study the clot sensitivity and as a marker for massive blood transfusion. The results of tPA-challenged TEG assay will not be used for any clinical decision or research subject assignment. At the moment there is no plan to submit tPA-challenged TEG data to the FDA. This study blood and pleural fluid will be drawn by the phlebotomy service or medical team member (nurse or physician to draw pleural fluid) and will be collected by a professional research assistant (PRA) trained in both running the TEG assay and in processing of blood for plasma analysis. Blood and pleural fluid samples will be 3.5ml each.

Study blood will be drawn prior the intervention and then for 3 sequential days after (for a total of 4 draws). This blood will be assayed by TEG with and without the t-PA challenge. This modified TEG assay (t-PA challenge) is completed by taking 500 microliters of patient blood out of the citrated tube and adding it to a pre made

glass container with lyophilized t-PA. This blood is mixed with a defined concentration of t-PA is then added to a TEG cup for analysis. This will quantify the patient's systemic blood to fibrinolysis resistance. In addition to the blood draws, pleural fluid will be drawn from the patient's chest tube in the morning prior to the intervention, and then after the intervention for 3 days (same days that blood samples are obtained, for a total of 4 pleural fluid samples). Pleural fluid samples will only be drawn from chest tubes already in place. In the event the chest tube is removed prior to 3 days post-intervention pleural fluid samples will be unattainable. The pleural fluid would otherwise be discarded as human waste. We will also conduct a novel assay to determine if the pleural space content is fibrinolytic resistant. This will be accomplished by an ex vivo diluting of the patient's blood (from the collected citrated tube) by 25% with normal saline and conducting a t-PA challenge versus a 25% dilution of the patient's blood (from the collected citrated tube) with their pleural fluid. The relative differences in the lysis at 30 minutes between these two assays will give a crude estimate of fibrinolytic inhibition. Remaining blood after TEG analysis will be spun down to plasma and flash frozen for future measurements, such as elastase activity and a targeted cohort for proteins related to coagulation with proteomic analysis. These results paired with proteomic analysis will enable correlations between fibrinolysis resistance and relative protein concentrations to identify potential mechanistic culprits driving fibrinolysis resistance. This study blood will be collected by PRA (drawn by the nurse and handed off to the PRA) trained in both running the TEG assay and in processing blood for plasma analysis.

Data collection will be done prospectively by a member of the research team. Data

will be stored in a secure excel sheet accessible only to the study team members.
Randomization

Intervention

VATS decortication
Vs.
tPA and DNASE per MISTII protocol

D. Description, Risks and Justification of Procedures and Data Collection Tools:

The adverse events of the standard of care fibrinolytic therapy include pain, fever, bleeding, and failure to effectively clear infection from the pleural space requiring

surgery, which tend to be higher risk due to disease progression. The VATS decortication is a slightly more invasive procedure, as it requires general anesthesia and single lung ventilation. Complications from surgery include injury to lung causing an air leak, bleeding, pain, and need for conversion to an open operation. The VATS surgery uses small holes in the thoracic cavity that are similar in diameter to a chest tube. This requires 1 or 2 additional holes in the chest cavity compared to the patients who already have one chest tube receiving fibrinolytic therapy. The benefits of VATS over fibrinolytic therapy are reduction in chest tube time and overall reduction in hospitalization time. In children VATS reduced the requirement of a chest tube by 3 days and associated with hospital discharge 3 days earlier with resolution of symptoms 3 days earlier. This is logical as the chest is cleared of all infected material with the VATS operation, while fibrinolysis is dependent on the medication breaking down all of the loculated fluid collections. The second benefit may be a reduction in cost to the patient, and improvement in resource utilization of the hospital. Three days of hospitalization out weighs the cost of the operating room. All clinical outcomes will be monitored by a research team member who will be collecting blood on a daily basis for 3 days post intervention and inputting data into a RED CAP data bank designed for the study. As this study is associated with an operative arm a data safety monitoring board (DSMB) will be created to assess patient outcomes after enrollment of 10 patients or once a year, even if enrollment has not increased by 10. This will not include an interim analysis on primary outcome, as this will decrease power and necessitate additional patients for enrollment. We anticipate that roughly 2 patients per month will be eligible for enrollment in this study and would expect completion of the study within 18 months.

E. Potential Scientific Problems:

This study is established as a pragmatic study as it is anticipated that some patients would prefer conservative fibrinolytic therapy to surgery. We have adjusted for this in our power calculation (see below). In addition the timing of availability of the operating room staff is not predictable. There may be a delay in taking the patient to the operating room. The importance of performing this study is that it is perceived that fibrinolytic therapy should be the standard of care for treating these patients. However, pediatric literature supports that optimal care of these patients may be an early surgical intervention. This is similar to an operative intervention for appendicitis. While it is possible to treat patients with appendicitis with antibiotics and avoid surgery, it results in longer hospitalizations, in addition if medical treatment fails the appendical perforation can result in life threatening sepsis and require surgery or additional procedures. This parallels complicated parapneumonic infections, in which surgery can be avoided, but result in prolonged hospitalization and if fibrinolytic therapy fails, surgery becomes a riskier endeavor.

F. Data Analysis Plan:

Power analysis

Using the pediatric literature assume effect size of reduction in 3 days of hospitalization requirement with variability of 2.3 days with alpha of 0.05 and 1:1 group allocation would require 12 patients per arm (24 total) to power the study to 80%. Anticipating up to 30% of patients may decline surgery we would seek to enroll 17 patients per arm. Will conduct an analysis based on intention to treat (included patients who declined surgery) in addition the treatment the patients received.

	STK	VATS	P
Post-therapy days of O ² support	2.3±1.4	2.1±2.0	0.911
Afebrile days after intervention	3.9±2.1	3.4±2.4	0.782
Analgesia doses	22.1±18.9	25.4±13.1	0.561
Chest tube removal time	9.48±2.50	6.56±1.55	0.0001
Duration of hospital stay	10.37± 2.29	7.41±1.45	0.0001
Duration of symptoms after intervention	6.78±1.69	3.78±1.25	0.0001
Fluid drainage			
Initial drainage amount	394.93±220.65	379.19±230.14	0.786
Postoperative drainage amount	850.59±301.91	865.78±444.41	0.884

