Bacterial and neutrophil activity acidify the fluid, consume glucose, increase protein content, and release lactate dehydrogenase (LDH) from cellular apoptosis and necrosis. The environment now becomes hypercoagulable because of the integrated responses of the innate immune and coagulation systems.(7, 8) These findings are directly relevant to the evolution of complicated effusions because the exuberant fibrin deposition is a concerted effort to control progressive infection. The final state of a complicated effusion is referred to as the organization phase (days 10–21). Fibroblasts migrate into the pleural space and create a dense fibrotic lining of the visceral and parietal surfaces. This phase is thought to be driven by regenerative cytokines, for example, transforming growth factor-[beta] and platelet-derived growth factor released primarily from activated mesothelial cells.(9) The net result is a progressive rind that encases the lung, reducing ventilatory capacity and sequestering bacteria.

Risk Factors and Bacteriology of Pleural Space Infection

There are over a million patients hospitalized for pneumonia a year and 10% of these patients will develop a pleural space infection(10). Patients who present to the hospital with pneumonia have an increased risk for pleural space infection if they have a history of IV drug use and alcohol abuse(11), age less than 60(12), and male gender(13). Nosocomial pneumonia have a higher rate of pleural space infection and have reported needs for operative intervention in up to a third of patients(14). The incidence of pleural infection in trauma patients with thoracic injuries is around 3%.(15) Risk factors for developing a post-traumatic empyema include multiple rib fractures, thoracostomy tube placed in the emergency department, and underlying pulmonary contusion. Another risk factor is placement by non-surgical specialty (16). This has clinical significance as a retained post-traumatic hemothorax has the highest risk for empyema, with an infection rate of over 25%(17).

A Gram stain and culture of the pleural fluid is often beneficial in directing management in pleural space infection, although 20% to 40% of the time, there is no reported identifiable pathogen.(12, 18, 19). However, the patient's history is often helpful when directing empiric antibiotics while waiting for gram stains and cultures to finalize. In empyema associated with community-acquired pneumonia, the most

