Those patients with fluid tested in the chest space concerning for pleural infection require empiric antibiotic treatment to cover suspected pathogens in addition to tube thoracostomy drainage. The exception is in patients with gross purulence aspirated from the pleural space that should undergo prompt operative decortication. The optimal size of the chest tube remains debated,(33, 34) but a 18F seems effective in removing this hypercoagulable fluid. This is a grade B recommendation. These smaller chest tubes are associated with less chest wall pain than blunt dissection–inserted tubes, without compromise in clinical outcome. The position of the chest tube, however, is important.(34) The tube should be placed in the posterior (dependent) pleural space and not within a pulmonary fissure. We have observed that the typical “trauma” chest tube introduced through the fifth intercostal space (ICS), at the mid–axillary line, favors fissure placement. Consequently, we recommend ultrasonography-guided tube insertion via the sixth intercostal space. But this is based on our unpublished experience. A Gram stain and culture of the pleural fluid should be obtained at the time of tube thoracostomy to differentiate the organism, although as previously mentioned up to 40% of the time no pathogen may be found. More recent techniques such as countercurrent electrophoresis, latex agglutination, or bacterial DNA detection by polymerase chain reaction could in theory improve pathogen identification, but are not currently standard of care in the clinical setting.(30)

After tube placement vigilant follow up of chest tube output and changes in radiographic appearance are critical. Pleural collections persisting for more than 24 hours warrant prompt computed tomographic (CT) imaging for evaluation of the entire thoracic space.(9, 29). Delay in diagnosis of an undrained simple fluid collection allows progression to a complex multilocular process and the final organization stage.(35) As Sahn and Light(28) stated in 1989, “the sun should never set on a parapneumonic effusion”; early diagnosis and treatment of complicated pleural infection is essential for optimal outcomes. CT images are crucial for the next step in the management of pleural space infections that have not resolved with tube drainage as this dictates operative versus fibrinolytic therapy.

Fibrinolysis Therapy for Treating Pleural Space Infections

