There are no randomized control trials evaluating VATs vs. fibrinolytic therapy in adults. However in adolescents a small trial demonstrated equivalency in fibrinolytic therapy and VATS in clearing infection, but the surgical intervention group had 3 fewer days with a chest tube and 3 fewer hospital days(55). This is important to take into the context of the patient's physiologic status. There is a need for a prospective randomized control trial to determine if VATS or fibrinolytic therapy is the optimal treatment of patients with complicated parapneumonic effusions who are physically fit to undergo surgery. In addition there are also patents that should proceed to decortication and avoid attempts at fibrinolysis therapy. Multiloculated empyema with an established pleural peel evident on CT scanning should undergo prompt VATS.(48) Although "medical" VATS using local anesthesia has been reported,(56) the standard procedure is lateral decubitus positioning with dual lung ventilation to facilitate comprehensive evaluation of the involved pleural cavity and systematic decortication. A key maneuver is to enter the pleural space without injuring the underlying lung because of extensive pleural adhesions. An initial incision in the upper thorax, where the empyema is least developed, is usually the safest strategy. In most cases, we have used the existing chest tube site to free the lung for placement of the initial port. With the thoroscope in position and the lung at least partially deflated, additional working ports are added under direct vision. The sites for these ports are chosen to match the chest wall entrance of the chest tubes after VATS.

The objectives of VATS are to unroof all loculated collections, including those in the fissures, and to free the lung of the visceral pleural fibrous encasement.

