Usually, the decortication is initiated in the upper lobe, where the process is more limited, and ultimately, the fibrous debris is removed as much as possible from the lung surface to enable re-expansion. Dissection must be done carefully on the mediastinal side to avoid injury to the phrenic nerve and pulmonary vasculature. Similarly, clearing the diaphragm must be done cautiously to avoid perforation. In fact, the diaphragm does not need to be systematically debrided as long as the lower lobe is freed. After extensive decortication, the thorax is usually drained with three relatively large chest tubes (28F) to facilitate removal of debris and blood associated with the procedure. The most inferior tube is usually an angled tube positioned in the posterior dependent recess of the chest.

In the event of a dense fibrous peel that precludes clearance via VATS, a limited lateral muscle-sparing thoracotomy (“mini thoracotomy”) is performed to accomplish decortication. Transecting the posterior rib facilitates exposure of the fibrous cavity. Advanced empyemas often require scalpel incision to free the lung for re-expansion; inspection of the lung with periodic re-inflation should be done to avoid extensive pulmonary parenchymal air leaks. In the unusual case of a chronic empyema, a standard posterolateral thoracotomy is required. Often, the safest approach is to develop an extrapleural plane and directly enter the empyema cavity before any further thoracic dissection is done. After these extensive decortications, the thorax is drained with three relatively large chest tubes (28F), and the most inferior tube is usually an angled tube positioned in the posterior dependent recess of the chest. Occasionally, these tubes are simply transected to provide external drainage for outpatient management of extended processes.

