Treatment of an advanced process caused by a necrotic infected lung with associated major air leaks in a severely immunocompromised patient warrants open thoracic drainage. The Eloesser flap, thoracic cavity marsupialization via segmental rib resection and suturing the skin to the underlying parietal surface, has been the standard for these complicated cases.(57) But recently, simple open drainage with suturing the skin margin to the chest wall, thoracostomy, and the application of a vacuum-assisted wound closure has been popularized.(58, 59) Ultimately, some of these wounds will heal by secondary intention, and the remaining can be closed with thoracomyoplasty.(60)

Significance

Infection of the pleural space is a morbid condition requiring prompt intervention. The keys to optimal care in these patients are 1) early identification 2) antibiotics and 3) clearance of infection from the pleural space. When a chest tube has incompletely drained the pleural space within 24 hours CT imaging to better characterize the pleural space is essential. The Western Trauma Association has published a critical decision algorithm for determining which patients should proceed to decortication versus fibrinolytic therapy(61). It is important to note that there have been no randomized trials in adults comparing early VATs to fibrinolytic therapy in patients who can tolerate surgery. Future studies are warranted to address this gap in knowledge, as pediatric literature supports early decortication may be more cost effective and beneficial to the patient. Failure to appropriately treat pleural space

infection resulting in empyema results in highly morbid open operations requiring prolonged hospitalization and lengthy recovery.

III. Preliminary Studies/Progress Report:

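### The written entry rule in IV.B can randomise to fibrinolysis a patient whose CT shows multiloculated empyema with a peel, a group the protocol's own background sends to prompt VATS

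*Combined protocol and SAP*

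**What the plan says.** **Background (Section II).** Surgical Decortication says that some patients "should proceed to decortication and avoid attempts at fibrinolysis therapy" and goes on: "Multiloculated empyema with an established pleural peel evident on CT scanning should undergo prompt VATS". Early Management of Pleural Space Infection gives CT the deciding role for infections that have "not resolved with tube drainage as this dictates operative versus fibrinolytic therapy". Significance adds that, when a tube has not cleared the space within 24 hours, "CT imaging to better characterize the pleural space is essential".

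**Eligibility (IV.B).** If an effusion persists 24 hours after tube insertion, "the patient may then undergo CT scan to characterize the effusion". Patients are then approached for consent and randomised under this rule: "If CT scan is done and confirms a loculated fluid collection or if an additional CXR is grossly abnormal, despite chest tube drainage". Eleven exclusions follow. The two nearest to the point are frankly purulent drainage, which is noted as needing an operation in any case, and pulmonary symptoms for more than 14 days before admission. Peel, rind and organised stage are not mentioned.

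**Procedures (IV.C).** The standard-of-care paragraph says that patients with persistent collections *will* have a CT. Study Procedures times the start of fibrinolysis from that CT. Neither says what happens if the CT shows a peel.

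**The concern.** The background names a CT picture for which the choice between the arms is not open, and the entry rule does not carry it through. Any loculated collection on CT qualifies, and a multiloculated collection with a peel is loculated. IV.B can also be read as allowing entry on a chest film alone, in which case the finding that matters may never be looked for.

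What is at stake is mainly the safety of individual patients. A patient allocated to fibrinolysis receives a three-day course, and IV.D and IV.E both describe surgery after failed fibrinolysis as riskier. IV.A records secondary operations as adverse events, and IV.D has a safety board review outcomes after every 10 patients or yearly. Both act after allocation and do not prevent it.

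A secondary matter is applicability. The trial is meant to inform a choice between two treatments, and patients for whom the protocol regards that choice as settled add little to the answer.

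**Working it through.** The plan gives no figure on this point, so the check is mostly a comparison of texts.

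**1. Does an exclusion name the group?** No. All 11 were read; none refers to peel or to the organised stage.

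**2. Does the frank-pus exclusion remove it?** In part. That exclusion is judged on the drained fluid, whereas the background rule is a CT finding. A patient can have the CT picture without frank pus in the drain.

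**3. Does the 14-day limit remove it?** In part. Section II, under Evolution of Pleural Space Infection to Empyema, states: "The final state of a complicated effusion is referred to as the organization phase", and dates that phase to days 10 to 21. The limit counts prehospital days only, and entry comes at least 24 hours after tube insertion, so a patient at the limit is at symptom day 15 or later when randomised. Two cautions apply. The protocol does not say when day 0 of the phases falls, so the two clocks may not align. And reaching day 10 does not by itself mean an established peel.

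**4. Is the CT always available?** IV.B says *may* and adds a chest-film route; IV.C says *will* and starts fibrinolysis within 24 hours of the CT. A patient entered on film alone would have no CT from which to time treatment.

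**5. Exposure under assumed rates.** Inputs: 17 patients in the fibrinolysis arm (IV.F) and an assumed peel rate *p* among entrants, which the documents do not give. Expected number = 17*p*; chance of at least one = 1 − (1 − *p*)^17.

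| Assumed *p* | Expected among 17 | Chance of at least one |
|---|---|---|
| 2% | 0.34 | 29% |
| 5% | 0.85 | 58% |
| 10% | 1.7 | 83% |
| 30% | 5.1 | 99.8% |

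The 30% row is an outer bound for illustration; nothing in the documents supports a rate that high after the two partial exclusions. The table measures exposure, not harm.

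**6. Recruitment if these patients are screened out.** Inputs: roughly 2 eligible patients a month and 18 months (IV.D), and 2 × 17 = 34 places. Without the exclusion, 34/2 = 17.0 months. Eighteen months yields 2 × 18 = 36 patients, so up to 1 − 34/36 = 5.6% can be screened out within the planned time. At 10%: 34/(2 × 0.9) = 18.9 months, 34/0.9 = 37.8 assessed, 3.8 screened out. At 30%: 34/(2 × 0.7) = 24.3 months, 34/0.7 = 48.6 assessed, 14.6 screened out. This assumes that every eligible patient consents and that the 2 a month include peel patients.

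**The case against.** **The frank-pus exclusion may already cover the group.** The background rule requires empyema as well as peel, and the section on diagnosis uses empyema as a synonym for gross purulence. On that usage most of the group is already out. But the section on fibrinolysis speaks of early empyema treated with fibrinolytics, so the word is not confined to gross pus. The objection makes the remaining group smaller; it does not empty it.

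**The peel sentence is cited background, and the trial is pragmatic.** The paediatric randomised trial cited for comparing the two treatments covers, by its title, stage II and III empyema, so late-stage disease may have been randomised before. This is fair, but IV.E ties pragmatism to patient preference and operating-room availability. Nowhere does the protocol say that peel patients are included on purpose, and it does not reconcile such inclusion with its own background.

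**The missing figure may hold a peel branch.** It may, and this stands as a caveat. The written eligibility rule would still need to agree with it.

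**The CT conflict may be only wording.** Largely so. The case for closing the film-only route is consistency with IV.C and the need for a CT to read for peel, not a general preference for CT.

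**A stronger reading: a biased result.** A reader might infer that peel patients would tilt length of stay in favour of VATS. The documents do not support this. Peel can lengthen the surgical stay too: under Surgical Decortication, "In the event of a dense fibrous peel that precludes clearance via VATS", a limited thoracotomy follows, and advanced empyemas carry a risk of air leak. Neither the size nor the direction of an effect can be derived.

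**Conclusion.** The point holds in a limited form. As written, IV.B can randomise to fibrinolysis a patient with a CT picture that Section II sends to prompt VATS. The exclusion list already applies the same logic to frank pus, so leaving out peel looks like a gap rather than a choice. It should be corrected, with medium confidence.

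The size is unknown and may be small. The patients at issue are those with this CT picture, no frank pus and 14 days or less of prehospital symptoms, and every peel rate used above is an assumption. A reader might also infer that such patients are common, or that the protocol never requires a CT. Neither follows: no rate is given, and IV.C does state that the CT will be done. The conclusion rests on the written text, with the figure in IV.C not available.

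**What to change.** 1. Add to the exclusions in IV.B: *multiloculated empyema with established pleural peel on pre-randomisation CT (proceeds to VATS)*. The treating team judges this from the CT that IV.C already describes, and these patients are logged as screened out. The protocol sets no threshold for an established peel, so a one-line working definition would help different readers agree.
2. In IV.B, change the CT from *may* to *will*, so that it agrees with IV.C and no patient is randomised on a chest film without a CT read for peel.
3. If the figure in IV.C already shows a peel branch, make the eligibility text match it.

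**Cost.** One CT reading per patient before randomisation, and somewhat slower recruitment: within 18 months if up to 5.6% are screened out, about 19 months at an assumed 10% and about 24 at 30%. No extra CTs are needed if IV.C is followed. Otherwise, each 10% of the 38 to 49 patients assessed who would have entered on film alone adds about 4 to 5 CTs (0.1 × 38 = 3.8; 0.1 × 49 = 4.9); the documents do not give that share.
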